3.3 Step-down Procedure

All efficacy evaluations will be conducted using the ITT population in the 3 nested HRD subgroups, unless otherwise specified:

- 1. **tBRCA:** Patients with a tBRCA mutation per the CTA.
- 2. HRD (tBRCA or non-tBRCA LOH+): Patients who are found to have a BRCA mutation per the CTA or do not have a BRCA mutation, but have tumor genomic LOH $\ge 16\%$

3. **ITT Population**

The primary and key secondary endpoints will be tested among the tBRCA, HRD, and ITT subgroups using an ordered step-down multiple comparisons procedure. invPFS in the tBRCA subgroup will be tested first at a one-sided 0.025 significance level. If invPFS in the tBRCA subgroup is statistically significant then invPFS will be tested in the all HRD subgroup followed by invPFS in the ITT population. Continuing in an ordered step-down manner, the remaining secondary endpoints will be tested at the one-sided 0.025 significance level in the tBRCA, HRD, and ITT subgroups. Once statistical significance is not achieved for one test, the statistical significance will not be declared for all subsequent analyses in the ordered step-down procedure.

The primary and secondary efficacy endpoints will be evaluated in the non-nested, nonoverlapping subgroups of tBRCA, non-tBRCA LOH+, non-tBRCA LOH-, and non-tBRCA LOH unknown in order to ensure that the results in the HRD and ITT subgroups are not solely driven by the results in the tBRCA subgroup. In order to claim a significant result in the HRD subgroup, the size of the estimated effect in the non-tBRCA LOH+ subgroup should be clinically relevant and should be at least as large as what would be needed to achieve ''statistical significance'' in an analysis conducted in the entire HRD population. Similarly, for the ITT results to be considered significant and not solely driven by the results of the tBRCA or HRD subgroups, the size of the estimated effect in the non-tBRCA LOH- and non-tBRCA LOH unknown subgroups should be clinically relevant and should be at least as large as what would be needed to achieve ''statistical significance'' in an analysis conducted in the entire ITT population.

3.4 BRCA Subgroups

The tumor tissue-based CTA used in this study identifies sequence variants in the *BRCA1* and *BRCA2* genes; however, it does not distinguish between the mutation type, i.e., germline or somatic. In order to determine whether a *BRCA* mutation detected by the CTA is germline or

somatic, a central laboratory will sequence DNA extracted from blood. The germline and somatic designation for a tBRCA mutation will be based on the results of the central germline BRCA testing as described in Table 3.

Table 3.	Algorithm for Determine Origin of BRCA Mutation - Germline versus
	Somatic – in the tBRCA Population

CTA Result	Central Germline Blood Test Result	Designation
BRCA Positive	BRCA Positive	Germline ^a
BRCA Positive	BRCA Negative	Somatic
BRCA Positive	Not tested	Unknown

^a The same BRCA mutation should be detected in the CTA and central germline blood test result for a mutation to be considered germline.

4 PATIENT DISPOSITION

Patient disposition (analysis population allocation, randomized, discontinued, and primary reason for discontinuation) will be summarized using frequency counts, and the corresponding percentages.

5 PROTOCOL DEVIATIONS

Major protocol deviations will be identified via use of both central lab data and EDC data. The categories for major protocol deviations are in accordance with the ICH E3 guidelines¹ and will be identified prior to database lock. The deviations that will be deemed major fall under the following categories:

- Incorrect IP treatment compared to randomization
- Inclusion or exclusion criteria deviations
- Over-dose or under-dose of study drug
- Prohibited medications such as other anti-cancer medications
- Any other significant deviation that had the potential to affect the primary efficacy or safety of the patients

A listing with all the major protocol deviations will be presented.

6 DEMOGRAPHICS AND BASELINE CHARACTERISTICS

All demographic and baseline characteristics will be summarized for the ITT population.

6.1 Demographics

The demographic variables will be summarized with frequency tabulations that will focus on identifying differences between treatment groups in the extreme values of the distributions.

Descriptive statistics may also be used to summarize the quantitative variables. The demographic variables presented will include age, height, weight, gender, race, and ECOG performance status using the following categorizations:

- Age (years): \leq 50, 51-60, 61-70, 71-80, 81-90, > 90;
- Height (cm): ≤ 75, > 75-100, > 100-125, > 125-150, > 150-175, > 175;
- Weight (kg): $\leq 50, > 50-75, > 75-100, > 100-125, > 125-150, > 150;$
- Race: American Indian or Alaska Native, Asian, Black, Native Hawaiian or Other Pacific Islander, White, Other
- ECOG performance status: 0, 1
- Region: North America, Western Europe, Australia/New Zealand, and Israel

These categorizations may be adjusted if the majority of the data lies in only 2 or 3 of the categories.

6.2 **Baseline Clinical Characteristics**

The following variables will be summarized with frequency tabulations

- Time since diagnosis (months): > 12-24, > 24
- Type of Cancer (Epithelial Ovarian Cancer, Fallopian Tube Cancer, Primary Peritoneal Cancer, Other)
- Histological Classification (Serous, Endometrioid, Mixed, Other).
 - Stratification subgroups used in the treatment randomization:
 - tBRCA, nbHRD, biomarker negative
 - Best response to most recent platinum-based regimen (complete response [CR], partial response [PR])
 - Interval between completion of the penultimate platinum-based regimen and disease progression (6 to 12 months or > 12 months)
- Subgroups based on data recorded on eCRFs:
 - Best response to most recent platinum-based regimen
 - Interval between completion of the penultimate platinum-based regimen and disease progression (6 to 12 months or > 12 months)
- tBRCA and LOH subgroups based on the CTA
 - tBRCA
 - non-tBRCA LOH+
 - non-tBRCA LOH-
 - non-tBRCA LOH unknown
- tBRCA mutation (BRCA1, BRCA2) based on the CTA
- BRCA mutation origin (germline, somatic, or unknown) based on central laboratory and CTA results

Descriptive statistics may also be used to summarize these variables.

6.3 Medical History

Medical history events will be classified using the Medical Dictionary for Regulatory Activities (MedDRA) classification system version 19.1. Medical history data will be summarized using frequency tabulations by System Organ Class (SOC) and Preferred Term (PT).

7 STUDY DRUG EXPOSURE AND COMPLIANCE

The following variables will be summarized:

- Duration of treatment
- Number of patients with at least one dose reduction or interruption

The duration of treatment will be calculated as the number of days from the first dose of study drug to the day of the last dose of study drug +1. The number of patients with at least one dose reduction or interruption based on the dispensation log will be summarized with frequencies and percentages. In addition, the number of patients at each dose level will be summarized (i.e., 600 mg BID, 480 mg BID, 360 mg BID) in order to assess patients with multiple levels of dose reductions.

8 PRIOR AND CONCOMITANT MEDICATIONS

All concomitant treatments documented during the study period will be summarized in frequency tabulations for each randomized treatment group and overall. Prior/concomitant medication coding will utilize the World Health Organization (WHO) Drug Dictionary version 2016SEP01DDE (Enhanced).

Prior medications will only be presented in listings. Prior medications will be defined as those medications with both a start and a stop date that is before the day of the first dose of study drug administration. If either the start date and/or the stop date of the medication is missing so that it is unclear whether the medication was stopped prior to first dose of study drug administration then the medication will be included in the summary of the concomitant medications.

9 EFFICACY VARIABLES

9.1 Primary Efficacy Variable

The primary efficacy variable is investigator determined PFS (invPFS).

9.2 Secondary Efficacy Variables Included in the Step Down Analysis

- DRS-P subscale of the FOSI-18 instrument
- Total score of the FOSI-18 instrument
- Final Overall Survival (OS)

9.3 Secondary Efficacy Variables Not Included in the Step Down Analysis

- Interim OS
- Independent Radiology Review Determination of PFS

10 EFFICACY ANALYSIS

10.1 Primary Efficacy Analysis

The primary efficacy endpoint is PFS as assessed by the investigator (invPFS). The time to invPFS will be calculated in months as the time from randomization to disease progression +1 day, as determined by RECIST v1.1 criteria² or death due to any cause, whichever occurs first.

Only scans and deaths prior to the start of any subsequent anti-cancer treatment or within 90 days of treatment end date will be included in the analysis. Patients without a documented event of progression will be censored on the date of their last tumor assessment (i.e., radiologic assessment) prior to the start of any subsequent anti-cancer treatment or within 90 days of treatment end date. Patients who withdrew without a disease progression event and do not have any post-baseline tumor assessment will be censored at date of randomization.

The stratified log rank test will be considered the primary analysis for invPFS comparing rucparib to placebo. In addition, a stratified Cox proportional hazard model will be used to calculate the hazard ratio (HR) between the treatment groups. The following randomization strata are used to estimate the treatment effect:

- HRD classification by the CTA (tBRCA, nbHRD, biomarker negative)
- Best response to most recent platinum-based regimen (CR, PR)
- Interval between completion of the penultimate platinum-based regimen and disease progression (6 to 12 months or > 12 months)

10.1.1 Sensitivity Analyses for PFS

10.1.1.1 Censoring Distribution

Sensitivity analyses for invPFS will be performed to evaluate the impact of censored patients. The following analyses will be performed:

- According to the study protocol, tumor scans were to continue to be performed during follow up for patients who discontinued without a documented disease progression event by RECIST v1.1. As such, a sensitivity analysis will be performed in which all tumor scans or death events will be included for assessment of PFS even if the patient discontinued study treatment or initiated a subsequent anticancer therapy.
- Patients who discontinued the study due to clinical progression will be considered to have a PFS event on the date of their last dose of treatment

Additional sensitivity analyses may also be performed to evaluate the robustness of the study results. These analyses will be considered exploratory and will likely be motivated by the observed results.

10.1.1.2 Interaction Between Treatment and HRD Status

In order to further evaluate the effectiveness of rucaparib in the HRD subgroups, the interaction between treatment and HRD status will be tested using the Cox proportional hazards model for the primary endpoint of invPFs. The model will include:

- Indicator variable for treatment with rucaparib;
- Categorical variable for HRD status; and
- Interaction between treatment and HRD status.

The HRD status is defined as the following mutually exclusive subgroups: tBRCA, non-tBRCA LOH+, non-tBRCA LOH-, and non-tBRCA LOH unknown. In addition, further exploratory analyses may be performed using the HRD definitions based on the mutation in Appendix A.

10.2 Secondary Efficacy Analyses Included in the Step Down Procedure

Secondary efficacy analyses will be based on nested populations (tBRCA, HRD, ITT). The multiple comparisons procedure presented in Section 10.1 will be used to control the type 1 error rate for the key secondary endpoints.

10.2.1 Disease Related Symptoms – Physical Subscale of the FOSI-18

The time to an event of worsening in the DRS-P subscale of the FOSI-18 will be defined as the time from randomization to a 4 point reduction in the DRS-P subscale. Patients without a documented event of a 4 point reduction will be censored on the date of their last adequate FOSI-18 assessment or date of randomization if no FOSI-18 assessments have been completed. For patients without a baseline FOSI-18 assessment their values will be censored at date of randomization.

The same statistical test used for the primary endpoint (i.e., stratified log rank test and a stratified Cox proportional model) will be used to compare rucaparib to placebo for this endpoint.

10.2.2 Total Score of the FOSI-18

The time to an event of worsening in the total score of the FOSI-18 will be defined as the time from randomization to an 8 point reduction in the total score. Patients without a documented event of an 8 point reduction will be censored on the date of their last adequate FOSI-18 assessment or date of randomization if no FOSI-18 assessments have been completed. For patients without a baseline FOSI-18 assessment their values will be censored at date of randomization.

The same statistical test used for the primary endpoint (i.e., stratified log rank test and a stratified Cox proportional model) will be used to compare rucaparib to placebo for this endpoint.

10.2.3 Independent Radiologic Review of PFS (irrPFS)

The time to irrPFS will be calculated in months as the time from randomization to disease progression + 1 day, as determined by the IRR or death due to any cause, whichever occurs first.

Only scans and deaths prior to the start of any subsequent anti-cancer treatment or within 90 days of treatment end date will be included in the analysis. Patients without a documented event of progression will be censored on the date of their last tumor assessment (i.e., radiologic assessment) prior to the start of any subsequent anti-cancer treatment or within 90 days of treatment end date. Patients who withdrew without a disease progression event and do not have any post-baseline tumor assessment will be censored at date of randomization.

The same statistical test used for the primary endpoint (i.e., stratified log rank test and a stratified Cox proportional model) will be used to compare rucaparib to placebo for this endpoint.

10.3 Secondary Efficacy Analyses Not Included in the Step Down Procedure

10.3.1 Overall Survival

The time to overall survival will be calculated in months as the time from randomization to date of death due to any cause. Patients who are still alive will be censored on the date of their last available visit or last date known to be alive.

It is anticipated that the data for overall survival will be heavily censored at the time of the primary endpoint analysis. In order to adjust for multiple analyses of overall survival at a later stage, a stopping rule will be applied. The Haybittle-Peto^{3, 4} stopping rule will be applied where an overall survival result with a p-value <0.001 can be used to claim superiority of rucaparib compared to placebo. This means that a p-value <0.05 can be utilized at the final analysis which is projected to be once 70% of the death events has been collected.

The same statistical test used for the primary endpoint (i.e., stratified log rank test and a stratified Cox proportional model) will be used to compare rucaparib to placebo for this endpoint.

10.3.2 Population PK: Individual Model Parameter Estimates of Rucaparib and Covariates Identification.

A population PK analysis will be performed and documented in a separate report.

10.4 Exploratory Endpoints

Exploratory endpoints will be presented separately for the three nested analysis populations (i.e., tBRCA, HRD, and ITT population). The exploratory endpoints include change in CA-125 level, tumor response, and DOR in patients who had measurable disease per the investigator at baseline. The purpose of the exploratory endpoint is to further explore the efficacy. No multiple adjustment is performed for these analyses.

10.4.1 Change from Baseline in CA-125 Measurement

Analyses of changes and/or percent changes from baseline for CA-125 measured by the central laboratory will be analyzed for each scheduled post-baseline visit and for the final visit. Patients who do not have both a baseline measurement and at least one post-baseline measurement will not be included in these analyses.

At a given visit, the change and/or percent change from baseline for CA-125 will be compared between the randomized treatment groups using an ANCOVA using the treatment as a categorical factor and baseline measurement for the parameter as a continuous covariate.

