### **11.2.7.1 Change from Baseline in CA-125**

Analyses of changes and/or percent changes from baseline will be analyzed for each scheduled post-baseline visit and for the final visit for the CA-125 measurements from the central laboratory. Patients that do not have both a baseline measurement and at least one post-baseline measurement will not be included.

At a given visit, the change and/or percent change from baseline will be compared between the randomized treatment groups using an ANCOVA using the treatment as a categorical factor and baseline measurement for the parameter as a continuous covariate.

The association between the change from baseline in CA-125 measurements and invPFS will be evaluated using a Cox proportional hazards model. A measure of CA-125 kinetics such as the rate of change from baseline in CA-125 may also be associated with invPFS using a Cox model.

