3 GENERAL ANALYSIS CONVENTIONS

The summary tables will be presented by randomized treatment group (rucaparib vs placebo) within the nested populations outlined in the step-down procedure in Section 3.2 and other subgroups of interest.

Quantitative variables will typically be summarized using frequencies and percentages for appropriate categorizations and may also be summarized using descriptive statistics. For variables summarized with descriptive statistics, the following will be presented: N, mean, standard deviation, median, minimum, and maximum. Categorical variables will be presented using frequencies and percentages. The Kaplan-Meier methodology will be used to summarize time-to-event variables. If estimable, the 25th, 50th (median), and 75th percentiles will be presented along with the Kaplan-Meier estimates of event rates at 6-month intervals. The number of patients with events and the number of censored patients will also be presented. The stratified log rank test will be used to compare the PFS distributions between the randomized treatment groups. In addition, the Cox proportional hazards model will be used to estimate the hazard ratio between the randomized treatment groups. Months will be calculated as number of days divided by 30.4375.

All data will be used to their maximum possible extent, but without any imputations for missing data.

Unless otherwise indicated, baseline is defined as the last measurement on or prior to randomization.

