10.4.6 Patient Reported Outcome of EQ-5D

Analyses of changes and/or percent changes from baseline will be analyzed for each scheduled post-baseline visit and for the final visit for EQ-5D VAS. Patients that do not have both a baseline measurement and at least one post-baseline measurement will not be included.

At a given visit, the change and/or percent change from baseline will be compared between the randomized treatment groups using an ANCOVA using the treatment as a categorical factor and baseline measurement for the parameter as a continuous covariate.

10.4.7 Exploratory Endpoint: Association Between the Change from Baseline in CA-125 Measurement and invPFS

The association between the change from baseline in CA-125 and invPFS will be analyzed by adding the maximum decrease from baseline in CA-125 to the stratified Cox proportional model as a covariate in the model. The change or percent change will be analyzed both as a continuous variable and as a categorical variable depending on the data distribution.

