11 STATISTICAL / ANALYTICAL ISSUES

11.1 Statistical Hypothesis

The primary statistical hypothesis for this study is to test for differences in PFS within each of the nested populations (tBRCA, HRD and ITT) using a stratified log-rank test.

H0: HR (rucaparib/placebo) \geq 1. Ha: HR (rucaparib /placebo) < 1.

Stratification factors include:

- HRD classification tBRCA or nbHRD or biomarker negative) as determined by CTA
- Interval between completion of the penultimate platinum-based regimen and disease progression (6 to 12 months or >12 months)
- Best response (RECIST CR or PR [RECIST and/or GCIG CA-125] response) to platinum regimen received immediately prior to initiation of rucaparib maintenance therapy

All efficacy analyses will be based on the randomization strata given at randomization, however, a sensitivity analysis of invPFS may be performed using the actual strata if patients have been allocated incorrectly.

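### CA-125 and EQ-5D VAS are compared visit by visit among patients still observed, so later CA-125 contrasts are open to selection; separately, the models omit the randomization factors

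*SAP*

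**What the plan says.** For CA-125, SAP 10.4.1 states that changes and/or percent changes from baseline "will be analyzed for each scheduled post-baseline visit and for the final visit". At any one visit the arms are compared "using an ANCOVA using the treatment as a categorical factor and baseline measurement for the parameter as a continuous covariate". On who enters, it says: "Patients who do not have both a baseline measurement and at least one post-baseline measurement will not be included in these analyses". SAP 10.4.6 repeats the design for EQ-5D ("post-baseline visit and for the final visit for EQ-5D VAS") with the same two-term model and the same entry rule ("Patients that do not have both a baseline measurement and at least one post-baseline measurement will not be included"). Protocol 11.2.7.1 ("for each scheduled post-baseline visit and for the final visit") and 11.2.7.5 give the same scheme.

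On missing data, SAP Section 3 says: "All data will be used to their maximum possible extent, but without any imputations for missing data". No repeated-measures model is named for either endpoint.

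On strata, SAP 11.1 says: "All efficacy analyses will be based on the randomization strata given at randomization". The sentence goes on to allow a sensitivity analysis of invPFS with the actual strata. SAP 10.4.3 uses a stratified Cochran-Mantel-Haenszel test for ORR. SAP 10.4.4 and 10.4.8 to 10.4.10 use stratified log-rank tests for DOR, chemotherapy-free interval and time to subsequent treatment.

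Protocol 9.5.5.2 schedules CA-125 at screening, Cycle 1 Day 1, every third cycle thereafter (Cycles 4, 7, 10 and so on), at treatment discontinuation and when clinically indicated. Under Protocol 5.1.3, treatment ends at investigator-assessed RECIST progression. Under Table 3, note f, disease assessment after treatment continues only for patients who stopped for a reason other than progression or death.

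**The concern.** There are two distinct issues.

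**Selection.** A patient who has left the CA-125 schedule contributes nothing to later visit-wise models, whatever her earlier values were. The main reason for leaving is progression. Progression is related to CA-125: Protocol 5.1.3 calls for imaging when the GCIG CA-125 progression criteria are met, so the marker itself helps decide who leaves. If rucaparib delays progression, the two arms are filtered at different rates. At later visits the model then compares those who remain, and randomization no longer protects that comparison.

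**Precision and consistency.** The treatment-plus-baseline model has no term for HRD class, platinum interval or best response. These may be prognostic, and the neighbouring exploratory endpoints are analysed with them.

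At stake is how the by-visit CA-125 and EQ-5D VAS results are read. If they are presented as randomized treatment comparisons at late visits, readers may give them more weight than the design supports.

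**Working it through.** **No stated figure.** The documents give no sample size, power or effect for these ANCOVAs, so there is nothing of that kind to reproduce. The planning medians in SAP 2.3 can be checked against their hazard ratios under exponential PFS: 6/12 = 0.50, 6/10 = 0.60 and 6/8.5 = 0.706, against the stated 0.50, 0.60 and 0.70. The medians are usable.

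**Inputs**
- Median PFS in months, placebo vs rucaparib: tBRCA 6 vs 12, HRD 6 vs 10, ITT 6 vs 8.5 (SAP 2.3)
- Group sizes at 2:1: tBRCA 60 and 120, HRD 100 and 200, ITT 180 and 360
- Visits: Cycle 7, 13 and 19 Day 1, which are weeks 24, 48 and 72 (28-day cycles, Protocol 9.5.5.2)
- Days per month: 30.4375 (SAP Section 3)

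**Formula.** Share progression-free at time t = 0.5^(t / median), with t = (cycle − 1) × 28 / 30.4375. This assumes exponential PFS and no other dropout.

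- Week 24: t = 168/30.4375 = 5.52 months. Placebo: 0.5^(5.52/6) = 52.9%.
- Week 48: t = 336/30.4375 = 11.04 months. Placebo: 27.9%.
- Week 72: t = 504/30.4375 = 16.56 months. Placebo: 14.8%.

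| Visit | Placebo | Rucaparib, ITT | Rucaparib, HRD | Rucaparib, tBRCA |
|---|---|---|---|---|
| Week 24 | 52.9% | 63.8% | 68.2% | 72.7% |
| Week 48 | 27.9% | 40.6% | 46.5% | 52.9% |
| Week 72 | 14.8% | 25.9% | 31.7% | 38.4% |

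In expected patients, placebo vs rucaparib:
- tBRCA: 32 vs 87 at week 24, 17 vs 63 at week 48, 9 vs 46 at week 72
- ITT: 95 vs 230, 50 vs 146, 27 vs 93

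These are attrition figures. They show how far the compared sets shrink and diverge; they do not measure bias.

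**Illustration of direction.** A simulation gave treatment no effect on the marker. It assumed a normal frailty with SD 1 on the log hazard, a conditional hazard ratio of 0.5, a placebo median of 6 months, and a correlation of 0.3 to 0.7 between frailty and marker change. The two-term ANCOVA was fitted only to patients still progression-free. The treatment coefficient was 0.08 to 0.18 SD at week 48 and 0.09 to 0.20 SD at week 72. In all randomized patients it was within 0.01 of zero. If a higher value is worse, the error runs against rucaparib. The frailty and correlation values are assumptions, not taken from the documents, so this shows that the mechanism works and in which direction, but not its size here.

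**Strata.** SAP 11.1 settles which version of the strata is used, as randomized or actual. It does not add a term to a model that 10.4.1 and 10.4.6 define with two terms. In the tBRCA population the HRD factor is essentially constant, because the same assay defines both, so about two factors are missing there and three elsewhere.

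**The case against.** Several points on the other side are sound.

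- **CA-125 does not simply stop at progression.** A sample is taken at discontinuation, and patients who stop for other reasons stay under disease assessment. CA-125 visits and 12-weekly scans coincide, so a patient found to progress at the week 24 scan will usually have a CA-125 value at about that time. If such values count towards the visit, the relevant share is that progression-free after the preceding scan: 73% vs 80-85% for week 24 and 38% vs 51-62% for week 48 (the same formula at Cycles 4 and 10). The SAP does not say how discontinuation values map to visits. This moves attrition back by one visit; it does not make the arms equal.
- **The final-visit analysis is the least selected comparison.** It keeps every patient with a baseline and any later value. Its weakness is that its timing differs by arm.
- **The stakes are low.** SAP 10.4 labels these endpoints exploratory, without multiplicity adjustment. The stated CA-125 objective, its association with invPFS, is handled in a stratified Cox model (SAP 10.4.7).
- **A mixed model has its own limits.** It implicitly extrapolates beyond progression and death, and an unstructured covariance would be fragile with about 9 tBRCA placebo patients at week 72.

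A reader might infer that omitting the strata causes the selection. It does not, and adding them would not cure it. A reader might also apply the percentages to EQ-5D. The current protocol lists EQ-5D only at screening and Day 1 of Cycles 1 and 2, and Section 9.5.6 says PRO collection was no longer required from Amendment 4, so neither its full schedule nor its attrition can be established.

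**Conclusion.** The point holds as a minor one. The visit-wise ANCOVAs use observed patients only. For CA-125, the plan's own medians imply progression-free shares of about 53% on placebo against 64-73% on rucaparib at week 24, 28% against 41-53% at week 48, and 15% against 26-38% at week 72. This rests on exponential PFS, no other dropout and the CA-125 schedule in the current protocol. Later contrasts are therefore open to selection bias.

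A stronger reading would be that the estimates are biased by a known amount or in rucaparib's favour. The documents support neither: the size depends on how closely CA-125 change tracks progression risk, which they do not give, and the illustration points against rucaparib if higher is worse. For EQ-5D VAS the same design weakness is present, but its extent is unknown.

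The missing randomization factors are a separate loss of precision and a departure from how the other exploratory endpoints are analysed. Nothing in the step-down procedure is affected.

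**What to change.** Analyse each endpoint with one mixed model for repeated measures.

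- **Terms:** treatment, visit, treatment-by-visit, baseline, baseline-by-visit and the as-randomized strata, leaving out the HRD factor in the tBRCA population. State in SAP 11.1 that the strata enter these models.
- **Data:** include discontinuation values, with a rule for mapping them to visits.
- **Visits:** report contrasts only at early, named visits with adequate numbers in both arms. Name a simpler covariance structure as fallback if the unstructured one does not converge.
- **Scale:** use log CA-125. Entry requires CA-125 below the upper limit of normal (Protocol 6.2, criterion 7), so percent change starts from a low base and is likely right-skewed. The present wording also leaves open whether change or percent change is used.
- **Reporting:** show the number of patients by arm at each visit. Keep the final-visit comparison as descriptive, with a note that its timing differs by arm.

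The cost is modest programming and reliance on data being missing at random given the observed values. That assumption is not guaranteed, but it is weaker than the one implicit in separate observed-case models. No new data are needed. Protocol 11.3 says all endpoints were summarized when the primary endpoint was unblinded, so for results already produced the model should be added as a labelled supportive analysis. If no re-analysis is done, the minimum is to call the by-visit results descriptive and give the numbers behind them.
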